### **2.5.2 control variables**

The control variables will be the peripheral muscle strength established by the handgrip test, by the maximum voluntary contraction test and by the peripheral muscle endurance test. In addition, we will use the mMRC , the quantified fatigue pictogram, the PCFS and the quality of life as control variables.

### **2.5.3 Exposure variables**

The exposure variables will be the 12-week, twice-weekly exercise program based on the Pilates method .

### **2.5.4 Confounding variables**

The length of stay and the degree of dysfunction acquired in the ICU may represent confounding variables. Thus, avoiding regression to the mean, inclusion in the study can only occur after 3 months (90 days) after hospital discharge. This is the time described to minimize eventual complications inherent to the immobility syndrome and homogenize the groups

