## 1.1 Introduction

Covid-19 has been described as a serious respiratory disease, which mainly affects the lower respiratory tract, coursing with pneumonia and SARS. In general, the course of the disease can range from mild (about 81% of cases) or moderate to severe (14% of cases) (MACHADO, *et al.* , 2020; RAGHU, WILSON, 2020) . However, about 5% have critical clinical conditions combined with other systemic complications, as a result of the morbidities acquired in the process, which cause important impacts on the functional and cognitive capacities of recovered individuals (PAHO/WHO, 2020)

In this context, the respiratory condition is one of the most affected in the process of infection by SARS-CoV-2, and such findings have been demonstrated by studies with very robust methodologies, that important fibrotic lung lesions emerged as the main consequences observed in individuals who had the most severe form of Covid-19 (GREVE, BRECH, *et al.* , 2020, HULL, *et al.* , 2020) . Still in this context, Raghu and Wilson (2020) were able to observe in their study that individuals, after hospital discharge, presented restrictive pulmonary sequelae, such as: the reduction of lung volumes and capacities, as well as diffusion alterations inherent to interstitial impairment, in addition to some important findings regarding small airway obstruction. Another consequence of SARS-Cov-2 infection on respiratory capacity is the damage generated in neural tissue by inflammatory events, causing loss of neuromuscular function, generating hypotrophy of the respiratory muscles (HADAYA;, BENHARASH, 2020; ZOUFALY, POGLITSCH, *et al.* , 2020) .

Another very important finding in post-Covid-19 individuals was also observed, is the musculoskeletal condition. In this sense, the authors Greve, Brech *et al.* . (2020) will describe in their study that in the first week of hospitalization, a loss of up to 20% of quadriceps muscle mass can occur in septic individuals in the ICU. Among the main findings, the authors point out that just being in bed for a week can generate a 30% reduction in muscle strength, followed by an additional loss of 20% each following week. In view of this, it is concluded that the loss of muscle mass and strength is closely

and directly associated with deficits in the functional capacity and daily activities of these individuals (CORRÊA, KARLOH, *et al.* , 2011; NUNES, HERVÉ, *et al.* , 2020) .

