### **1.1.8 respiratory disorders**

fibrotic normalities , previously associated with the idiopathic cause, are the main consequences left by the passage of Covid-19, so that its manifestations can result from any stage, being evidenced more frequently in cases that have undergone the most severe form of the disease. illness. Consequently, the lung damage caused by SARS-CoV-2 infection in the acute phase results from the combination of some expected clinical manifestations, such as: edema formation, alveolar release of epithelial cells and deposition of hyaline material in alveolar membranes . (POGLITSCH, *et al.* , 2020) . During the 2nd and 4th weeks, the lungs show signs of fibrosis, characterizing the next phase of the infection, where fibrin deposition occurs, infiltration of inflammatory cells and fibroblasts adjacent to the epithelial cells in the alveolar spaces (HULL, LLOYD, *et al.* , 2020) .

A little further on, during the 6th to 8th week, the lung tissue becomes fibrotic , in addition, bilateral lesions tend to be observed. In this context, Raghu and Wilson (2020) observed in their study that individuals, after hospital discharge, present restrictive abnormalities such as reduced diffusion capacity and small airway obstruction. Some authors also suggest that these abnormalities may be common in lung function, especially in individuals who have reached the most severe form of Covid-19, due to high inflammatory rates and pulmonary fibrosis.

Despite what is already evidence on the multisystem sequelae of Covid-19, several other studies are emerging around the sequelae left in the respiratory system after infection by the SARS-CoV-2 Coronavirus , suggesting that these may vary in individuals who have had it. mild, moderate or severe frames. The same authors also state that the resolution of the abnormalities may occur within the next 6 to 12 months after the infection, or even become permanent (HADAYA, BENHARASH, 2020) .

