### **2.3.2 Inclusion criteria**

1. Patients with a previous diagnosis of COVID-19, who required hospitalization and required invasive mechanical ventilation for at least 7 days and who were discharged between August and December 2021 to minimize regression to mean;
2. Both sexes;
3. Older than 18 years.

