## 2.8 Timeline

**Table 4: Execution schedule.**

step identification	Start (mm/yy)	Term (mm/yy)
Beginning of the course and designing the project	August/20	November/21
Project submission to the Research Ethics Committee	April/22	April/22
Methods training	April/22	April/22
patient recruitment	April/22	May/22
Execution of the Protocol	April/22	July/22
Data collection and tabulation	April/22	July/22
Data analysis	July/22	August/22
Preparation of the manuscript(s)	August/22	August/22
Final essay writing	August/22	August/22
defense exam	September/22	September/22
Changes guided by the examining board	September/22	September/22
Submission of manuscript(s)	September/22	October/22
Delivery of the final version of the final paper	October/22	October/22

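### The 90-day post-discharge rule excludes no eligible patient, and the confounders it is meant to handle are neither stratified nor adjusted for

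*Combined protocol and SAP*

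**What the plan says.** Section 2.5.4 says that length of stay and dysfunction acquired in the ICU may confound the results. The response is a minimum wait: "Thus, avoiding regression to the mean, inclusion in the study can only occur after 3 months (90 days) after hospital discharge". The same section says the interval limits complications of immobility and homogenises the groups. Section 2.3.2 makes a similar claim for the discharge window and admits patients "who were discharged between August and December 2021 to minimize regression to mean".

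Table 4 (section 2.8) schedules the "patient recruitment" step for April to May 2022, with ethics submission also in April 2022.

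On allocation, the Summary gives a 1:1 ratio and section 2.2 an electronic list from random.org. Neither mentions blocks or strata. Section 2.5.5 plans a general linear model with mixed design and names no covariate. Section 2.5.2 lists strength, endurance, mMRC and fatigue, together with "the PCFS and the quality of life as control variables". These are measures the trial takes before and after treatment. Length of stay, ventilation days and time since discharge are not among them.

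**The concern.** The protocol identifies two factors that could distort the comparison and treats them as dealt with by an entry rule. Three things look wrong.

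- If every patient who meets section 2.3.2 has already passed 90 days when recruitment opens, the rule changes nothing about who enters.
- The rule does not fit the task. A lower limit on time since discharge sets no limit on length of stay and does not spread it evenly between arms. Regression to the mean comes from selecting on a noisy measurement. The only entry criterion that cuts on a measured strength value is the grip exclusion in section 2.3.3, and neither the wait nor the discharge window alters it.
- Because the threat is recorded as handled, the two ordinary tools for it, stratified allocation and prespecified adjustment, are absent.

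At stake is the precision of a small trial, and how far a chance imbalance in ICU course or time since discharge can move the 12-week difference without the planned analysis correcting for it.

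**Working it through.** **The plan's own figure.** Section 2.5.1 uses d = 4.7/5.05 = 0.93, two-sided alpha 0.05 and power 0.80. A two-sample t calculation gives n = 19.16 per group, rounded up to 20, and 20 × 1.2 = 24. This reproduces. Section 2.3 gives 30 per group instead, so both sizes are carried below.

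**Does the rule exclude anyone?** Inputs: discharge 1 August to 31 December 2021 (section 2.3.2) and recruitment 1 April to 31 May 2022 (Table 4), taking first and last days of the named months.
- 31 December 2021 + 90 days = 31 March 2022, one day before recruitment can open.
- Shortest gap at entry: 31 December 2021 to 1 April 2022 = 91 days.
- Longest gap: 1 August 2021 to 31 May 2022 = 303 days.
- Eligible discharge dates removed by a 90-day minimum: 0 of 153. The minimum would have to be 92 days to remove one date, and then only for entry on 1 April.

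The spread of 303 − 91 = 212 days comes entirely from the discharge window and the recruitment period.

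**How large can chance imbalance be?** For any one baseline factor under unstratified 1:1 allocation, the standard error of the standardised difference between arm means is √(2/n). Probabilities are two-sided, by normal approximation.

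| | 24 per arm | 30 per arm |
|---|---|---|
| Standard error | √(2/24) = 0.289 SD | √(2/30) = 0.258 SD |
| P(difference > 0.25 SD) | 39% | 33% |
| P(difference > 0.5 SD) | 8.3% | 5.3% |

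As an illustration in days, assume uniform discharge and entry dates. The SD of time since discharge is then √((153² + 61²)/12) ≈ 48 days, so 0.5 SD is about 24 days.

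**What would that do to the estimate?** The documents give no correlation between these factors and the outcome, so r = 0.3 to 0.5 is assumed. The shift in an unadjusted difference is r × imbalance. For a 0.5 SD imbalance it is 0.15 to 0.25 SD. With the SD of 5.05 kg from section 2.5.1, that is 0.15 × 5.05 = 0.76 kg to 0.25 × 5.05 = 1.26 kg, against a target of 4.7 kg.

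**What would adjustment gain?** It reduces the residual SD by √(1 − r²), so d becomes 0.93/0.954 = 0.97 at r = 0.3 and 0.93/0.866 = 1.07 at r = 0.5.

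| Per arm | Power, unadjusted | Power, adjusted (r = 0.3 to 0.5) |
|---|---|---|
| 24 | 0.88 | 0.91 to 0.95 |
| 30 | 0.94 | 0.96 to 0.98 |

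The assumed r is the total correlation of the covariate with the 12-week outcome. Once baseline strength is in the model, the further gain from ICU variables will be smaller.

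**The case against.** The best reply is that the trial is randomised against a concurrent untreated control. Spontaneous recovery and regression to the mean act on both arms alike in expectation, and the stated significance level and confidence interval already allow for chance imbalance. This stands. A reader might infer that ICU stay and recovery stage bias the comparison, or are wholly uncontrolled; the documents do not support that.

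It can also be said that the rule is redundant rather than broken. Its aim of limiting immobility complications is met for every patient, because the dates already guarantee 91 days. That is fair. What fails is the claim about homogeneity and regression to the mean.

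Some control does exist. The before-and-after design uses each patient's own baseline, the baseline strength tests register dysfunction still present at entry, and the grip exclusion removes the weakest patients. None of these covers length of stay or time since discharge directly.

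Three further inferences are tempting and should be resisted.
- Section 1.1.8 says that "the resolution of the abnormalities may occur within the next 6 to 12 months after the infection". That passage concerns respiratory abnormalities, counts from infection, is worded as a possibility and allows for permanent damage. It does not show that muscle function is recovering spontaneously at 91 to 303 days after discharge.
- The figures in section 1.1, "a 30% reduction in muscle strength, followed by an additional loss of 20% each following week", describe acute loss in bed. They do not measure differences remaining months later.
- No section says that ICU stay sets the rate of later recovery, or calls recovery stage prognostic. Section 2.5.4 says only that the two factors may be confounders.

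**Conclusion.** The point holds in a limited form. On the planned dates the 90-day rule excludes nobody, and even a rule that did exclude patients could not balance length of stay or act on regression to the mean. No stratification factor or model covariate covers the named confounders. The consequence is unadjusted chance imbalance and lost precision, with no systematic bias. Even an imbalance of 0.5 SD would move the estimate by roughly 0.8 to 1.3 kg under the assumed correlations, well short of the 4.7 kg target. This is an inexpensive improvement that should be made; the trial's validity does not depend on it.

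The date result rests on the Table 4 schedule. It would change only if recruitment began before 31 March 2022, which the April 2022 ethics submission rules out. The imbalance probabilities need only the arm sizes and simple 1:1 allocation. The shift and power figures depend on the assumed correlations.

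**What to change.** - **Sections 2.5.4 and 2.3.2:** delete the statements that the 90-day rule and the discharge window homogenise the groups or avoid regression to the mean. The entry criteria themselves need not change for this point.
- **Section 2.5.5:** prespecify three covariates for the between-arm comparison: the baseline value of the outcome, days of invasive ventilation (or length of stay, from the clinical history taken under section 2.3.5), and days since discharge. Baseline cannot be both a repeated measure and a covariate, so write the adjusted comparison as the 12-week value on arm plus covariates.
- **Section 2.5.2:** keep the baseline strength, endurance and function measures, and add the two new variables. Dropping the existing list would discard the natural baseline covariates.
- **Section 2.2 (optional):** stratify the allocation list by ventilation days at a prespecified cut. This would not balance time since discharge, so the covariate is still needed.

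The cost is three degrees of freedom. With 48 patients, the residual falls from 48 − 2 = 46 to 48 − 5 = 43. Exact ventilation days must be recorded, where eligibility needs only confirmation of at least 7. No extra visits or patients are required.

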### **2.5.5 Statistical analysis plan**

Data analysis will be performed using the SPSS 23.0 program ( Statistical Package for Social Sciences ). Descriptive analysis will be performed for all variables (mean and standard deviation). General Linear Model ( GLMs ) with mixed design will be performed to compare treatment effect size between groups. The pairwise comparison comparisons ) will be performed to verify the mean difference between the Pilates Group and the Control Group in all variables in each period independently.

Intention-to-treat analysis was used using the *Last method. observation Carried Forward* (LOCF) for lost participant data. A significance level of 0.05 and a confidence interval of 95% will be adopted

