## Summary

**Introduction:** COVID-19 is an emerging pandemic disease caused by severe acute respiratory syndrome (SARS-CoV-2). Although most patients infected with SARS-CoV-2 are asymptomatic or have mild symptoms, some patients develop severe symptoms that can long-term impair their quality of life and functional capacity. SARS-CoV-2 is closely related to severe acute respiratory syndrome (SARS) with direct and indirect effects on several systems, especially the musculoskeletal system, in addition to the respiratory system. Some of these symptoms persist for a long time, called Post-Covid-19 Syndrome, directly interfering with the functional capacity and quality of life of these patients. Pilates exercises focus on breathing, postural symmetry, trunk stabilization, flexibility, joint mobility and strengthening through the full range of motion of all joints and not isolated muscle groups. **Objectives:** The objective of this study will be to evaluate the clinical and functional effects of a Pilates exercise program for patients with Post-Covid-19 syndrome after a period of intensive care admission and invasive mechanical ventilation. **Methods:** The study will be a clinical, randomized and controlled trial. 48 patients of both sexes, over 18 years of age, who have developed the severe form of COVID-19 and required at least 7 days of invasive mechanical ventilation will be recruited. Patients who currently require supplemental oxygen at home and who present motor, cognitive or neurological alterations that prevent the practice of Pilates will be excluded. They will be previously randomized in a 1:1 ratio by electronic system and blindly allocated to the intervention group that will perform an exercise protocol based on the Pilates method, 2x/week, for 12 weeks in therapeutic sessions of identical protocols lasting 60 min. All patients will be evaluated before and after for peripheral muscle strength and endurance, post-Covid-19 functional status, dyspnea, fatigue and quality of life. Data analysis will be performed using the SPSS 23.0 program ( *Statistical Package for Social Sciences* ). Descriptive analysis will be performed for all variables (mean and standard deviation). *General Linear Model* ( GLMs ) with mixed design will be performed to compare treatment effect size between groups. The *pairwise comparison comparisons* ) will be performed to verify the mean difference between the Pilates Group and the Control Group in all variables in each period independently. Intention-to-treat analysis was used using the *Last method. observation Carried Forward* (LOCF) for lost participant data. A significance level of 0.05 and a confidence interval of 95% will be adopted. **Results:** The expected results are based on the alternative hypothesis that Pilates exercises are clinically effective, improving functional performance, exercise tolerance, balance, reducing symptoms and improving the quality of life of patients with symptoms of Post-Covid-19 Syndrome.

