## **2.3 Sample**

The sample will consist of 60 participants, divided into two groups: an intervention group (n=30) that will do a 12-week program, 2x/week of Pilates method exercises , and a control group (n=30) that will not do any intervention for rehabilitation in the period.

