## 2.5 Data analysis

### 2.5.1 Sample size (calculation or justification)

The sample size calculation was done with the “ pwr ” package (CHAMPELY S, 2018) (R package , version 1.2-2, <https://CRAN.R-project.org/package=pwr> ). For the calculation, we considered the mean of 41.3, the standard deviation of 5.05 and a minimal clinically important difference of 4.7 kg between the means of maximum load in the maximal voluntary contraction test (OLIVEIRA IO, 2016) and power based on *Cohen 's model* of 0.8 with a standard deviation of 5.05. Assuming  $\alpha = 0.05$ ,  $\beta = 0.8$ , standard deviation = 5.05 and an effect size proposed by Cohen of 0.93.

This effect size " *d* " is calculated by:

$$d = [(Reference\ average + Minimum\ detected\ change) - reference\ average] / deviation - standard$$

$$d = [( 41.3 + 4.7) - 41.3] / 5.05 \Rightarrow d = 0.93.$$

*pwr* package . in R we have:

```
n = pwr.t.test ( n=NULL, d=0.93, sig.level =0.05, power=0.8, type=" two.sample ", alternative="
two.sided ")
```

$$n = 19.15925$$

$$d = 0.93$$

$$sig.level = 0.05$$

$$power = 0.8$$

$$alternative = two.sided$$

In this way, we use on=established and rounded up to the first integer immediately higher ( $n=20$ ) + 20% to cover any losses. Thus, the minimum number of patients needed in each group will be 24 patients.

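### Section 2.5.5 names no result as the treatment effect and no baseline covariate; a baseline-adjusted ANCOVA for the continuous outcomes would settle this and gain power at almost no cost

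*Combined protocol and SAP*

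**What the plan says.** Section 2.5.5 is the whole analysis plan; the Summary and Abstract repeat it. It has two parts. A general linear model "with mixed design will be performed to compare treatment effect size between groups" comes first. Pairwise comparisons follow, which "will be performed to verify the mean difference between the Pilates Group and the Control Group in all variables in each period independently". Lost participants are handled by last observation carried forward. No model term, contrast or covariate is named.

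The Summary gives two assessments: "All patients will be evaluated before and after for peripheral muscle strength and endurance", and likewise for the other outcomes. Baseline values will therefore exist.

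Two other sections come close to the subject:

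- Section 2.5.2 begins "The control variables will be the peripheral muscle strength established by the handgrip test" and goes on to list the remaining tests, mMRC, the fatigue pictogram, PCFS and quality of life. It does not say that these are baseline values or that any of them enters the model.
- Section 2.5.4 says "The length of stay and the degree of dysfunction acquired in the ICU may represent confounding variables", but deals with this by an entry rule (90 days after discharge), not by adjustment.

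The sample size in section 2.5.1 rests on an unadjusted two-sample t-test with "a minimal clinically important difference of 4.7 kg between the means of maximum load".

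**The concern.** With two arms and two visits, at least two results could be reported as the treatment effect:

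1. the Pilates-versus-control difference at 12 weeks, ignoring baseline, which is the closest match to the t-test in section 2.5.1;
2. the group-by-time interaction, which with two visits is the same as comparing change scores.

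A third, the group main effect of the mixed model, averages the two visits and so halves any effect that appears only at 12 weeks.

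Readings 1 and 2 estimate the same difference without bias, but they can give opposite verdicts on the same data, and the plan does not say which counts. Choosing after seeing both would raise the type I error. Each reading also wastes information over part of the range of pre-post correlations, and the documents give no correlation from which to choose.

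Comparing the arms in every period includes baseline, where the test examines only chance differences between randomised groups.

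**Working it through.** **Inputs.** From section 2.5.1: difference δ = 4.7 kg, SD σ = 5.05, two-sided α = 0.05, 20 per arm before losses and 24 after. From section 2.3: 30 per arm. Assumed, because the documents do not give them: the same SD before and after; pre-post correlation r = 0.3, 0.5, 0.7 or 0.8; 4 of 24 or 5 of 30 per arm lost; no mean change in the control arm.

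**The plan's own figure.** d = 4.7/5.05 = 0.93. The two-sample t-test at 80% power gives n = 19.16, rounded to 20; 20 × 1.2 = 24. This reproduces.

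**Standard errors, n per arm.**

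- 12-week contrast: σ√(2/n), df 2n − 2
- Group-by-time: σ√(2(1 − r))·√(2/n), df 2n − 2
- ANCOVA: σ√(1 − r²)·√(2/n)·√(1 + 1/(2n − 4)), df 2n − 3

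Example, n = 20, r = 0.5:

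- 12-week contrast and group-by-time: SE = 5.05 × √0.1 = 1.597, noncentrality 4.7/1.597 = 2.94, power 82%, CI half-width 3.23 kg.
- ANCOVA: SE = 5.05 × √0.75 × √0.1 × √(1 + 1/36) = 1.402, noncentrality 3.35, power 90%, CI half-width 2.84 kg.

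**Carrying forward.** With two visits, the carried value is the baseline. The expected difference falls to 4.7 × 20/24 = 3.92 kg (and to 4.7 × 25/30 = 3.92 kg at 30 per arm) whichever analysis is used.

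**Power (%) at r = 0.3 / 0.5 / 0.7 / 0.8**, from the noncentral t and simulation:

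| Per arm | 12-week contrast | Group-by-time | ANCOVA | First two disagree on significance |
|---|---|---|---|---|
| 20 completers | 82 | 68 / 82 / 96 / 99.5 | 84 / 90 / 98 / 99.7 | 26 / 21 / 19 / 18 |
| 24, 4 carried forward | 73 | 67 / 81 / 95 / 99.4 | 80 / 88 / 97 / 99.6 | 28.5 / 27.0 / 26.7 / 27.1 |
| 30 completers | 94 | 85 / 94 / 99.6 / 100 | 96 / 98 / 99.8 / 100 | 14 / 8.5 / 6 / 6 |
| 30, 5 carried forward | 82 | 77 / 89 / 98 / 99.9 | 88 / 94 / 99 / 99.9 | 23 / 19 / 18 / 18 |

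The group main effect at 20 completers has 43 / 38 / 34 / 33% power.

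**Type I error, 20 completers.** ANCOVA alone holds its level: 4.7 to 5.2% in simulation. Reporting whichever of the first two readings is significant gives 8.8 to 9.5%. This is an upper bound for a choice between those two and applies only if the choice is made that way. With the group main effect as a third option it is 10.8 to 11.5%.

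**Cost at the worst case.** At r = 0 and 20 completers, ANCOVA has 80.7% against 81.8% for the 12-week contrast.

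**Sensitivity.** Take 24 per arm, 4 carried forward, and completers in both arms also improving by an assumed 5 kg. Power is then 64% for the 12-week contrast, 59 / 72 / 89 / 97% (rounded) for group-by-time and 70 / 79 / 91 / 97% for ANCOVA. ANCOVA is still highest at each correlation (96.9% against 96.5% at 0.8).

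**The case against.** The strongest reply is that section 2.5.5 does imply an order: the mixed model is tied to the size of the effect, the pairwise tests only check mean differences, and the natural treatment term of such a model is group-by-time. One added phrase would then cure the ambiguity, and ANCOVA would be a preference. Part of this stands. Naming either reading would close the specification gap. But the text does not name one, and the sample size was calculated for the other contrast.

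The gain also depends on a correlation nobody has stated. If group-by-time was intended and r is 0.7 or more, ANCOVA adds under 2 points. That stands too. Each reading nevertheless has a region of real loss: group-by-time gives up 16 points at r = 0.3, and the 12-week contrast 18 points at r = 0.8 (20 completers).

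ANCOVA is not best under every assumption. With 4 of 24 carried forward and both arms' completers improving by 10 kg, it ties with group-by-time at r = 0.8 (about 79% each) and trails at r = 0.9 (91.7% against 93.4%). At 8 kg and r = 0.9 it is 98.0% against 98.5%. These are extreme assumptions, the shortfalls are under 2 points, and they lie outside the range of r claimed here.

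Section 2.5.2 may have been meant as a list of covariates, in translated text. As written it does not say so.

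Other definitions remain open: which hand's grip value is analysed (2.3.6.1), whether 1RM is analysed in kg or relative to body weight (2.3.6.2), and whether the endurance load is reset at 12 weeks (2.3.6.3). ANCOVA settles none of these.

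**Conclusion.** The concern holds. For the continuous outcomes, the plan leaves open which number is the treatment effect and makes no stated use of baselines that will be collected anyway. The candidate analyses are valid, so this is a fault of specification and efficiency, not of bias.

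On the plan's own 4.7 kg and SD 5.05, the two main readings disagree on significance in 18 to 26% of trials with 20 completers per arm, and in 27 to 29% with 24 per arm and 4 carried forward. ANCOVA is at or above both for assumed correlations of 0.3 to 0.8 in all four sample-size settings. At 20 completers its gain over the 12-week contrast runs from about 2 to 18 points, and over group-by-time from 16 down to 0.2. The order is the same under either sample size in the documents (24 per arm in 2.5.1, 30 in 2.3).

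The figures assume equal SDs before and after and describe one component, quadriceps load. They do not settle how the components of the primary outcome in section 2.4.1 are combined, and ANCOVA does not undo the dilution caused by carrying baseline forward. Both need separate answers. The point should be addressed before analysis.

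**What to change.** In section 2.5.5, write: *For continuous outcomes (grip strength, quadriceps 1RM, endurance time, SF-36 domains) the treatment effect is the Pilates-minus-control difference in 12-week means, with 95% CI, from ANCOVA with arm and the baseline value of the same outcome.*

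Then:

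- drop the between-group test at baseline;
- keep the mixed model as supportive, with group-by-time named as its treatment term;
- give PCFS, mMRC and the Fatigue Pictogram, which are ordinal, a baseline-adjusted ordinal method;
- note that Borg is recorded only during Pilates sessions (section 2.3.8), so it has no control-arm value and cannot be analysed this way;
- state in section 2.5.2 whether the control variables are baseline values and whether any enters the model.

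The cost is SAP wording and one degree of freedom. No new data are needed. If the pre-post correlation were near zero, about one point of power would be lost against the 12-week contrast.
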